Clinical Trial Protocol Synopsis

Protocol title : The impact of soiled airway management on CPR quality
Objectives : To evaluate the influence of soiled airway management on the quality of CPR
Background : Regurgitation is an adverse event common during cardiopulmonary resuscitation (CPR) and occurs in 20%-32% of patients experiencing out-of-hospital cardiac arrest (OHCA). It can impair ventilation, induce aspiration, and decrease survival to hospital discharge. Gastric fluid in the airway obscures the laryngeal view, thereby considerably decreasing the first-pass success of endotracheal intubation (ETI) by paramedics. A human cadaver study reported that ETI outperforms other airway management devices, such as the i-gel, laryngeal mask, and laryngeal tube, in preventing aspiration when regurgitation occurs during CPR. However, ETI is also associated with multiple and prolonged CPR pauses. Compared with the use of supraglottic airway (SGA) devices, ETI results in more hands-off time during CPR. Recent randomised clinical trials have revealed that airway management with an SGA device provides superior outcomes to those of ETI in patients with OHCA. However, ETI remains the preferred management strategy for an airway affected by regurgitation in patients with OHCA. Current guidelines focus on the quality of CPR because it is a key determinant of survival in patients with OHCA. However, evidence regarding the impact of regurgitation during ETI on CPR quality is limited. This manikin simulation study assessed CPR quality during ETI in airways with and without regurgitation.
Study Design : A prospective compare study
Methods : This is a prospective compare study. 54 EMT-Ps, are involved to evaluate the impact of airway management on CPR quality. The Study uses SALAD training tool for training. The SALAD training tool include Nasco Intubation CPR manikin, which could vomit by pumping liquid into distal esophagus, and HQCPR feedback machine. Two scenarios were simulated. CPR and ETI in an airway with regurgitation (oropharyngeal regurgitation scenario) and CPR and ETI in an airway without regurgitation (clean airway scenario). All EMT-Ps were assigned to participate initially in one of the scenarios. After all EMT-Ps had finished the first scenario, they switched to the other. Three EMT-Ps formed a resuscitation team and played one of the following roles: airway manager, first compressor, or second compressor. In each scenario, each EMT-P was required to take a turn playing all three roles. During each simulation, the airway manager performed BVM ventilation, and the first and second compressors alternately provided chest compression for every five cycles of CPR, with a compression-to-ventilation ratio of 30:2. After the first five cycles of CPR, the airway manager was asked to perform intubation during

the ongoing chest compression to minimise intubation-associated interruption of chest compression. If necessary, the airway manager could request a pause of the ongoing chest compression. If intubation was not successful, the airway manager performed BVM ventilation twice and then reattempt intubation. After intubation, the airway manager used the BVM to check the lung distention to confirm successful intubation. Each simulation was ended after successful or failed intubation. Failed intubation was defined as either oesophageal intubation or three unsuccessful attempts.

The primary outcomes were CPR quality metrics, namely chest compression fraction (CCF), chest compression depth, chest compression rate, and longest interruption time. The secondary outcomes were the intubation success rate and intubation time.

Each CPR-intubation sequence comprised two segments: a compression segment and a hands-off segment. Presents the rules for determining the start and end of a CPR-intubation sequence. CCF was defined as the proportion of time spent on chest compression in each CPR-intubation sequence. The longest interruption time was defined as the longest hands-off duration in each sequence. An intubation attempt was defined as the insertion of the laryngoscope blade into the mouth and its subsequent withdrawal from the mouth. Intubation time was defined as the period between the start and the end of an intubation attempt. The time spent checking the endotracheal tube position by manual ventilation through the endotracheal tube was not included in the CPR-intubation sequence.

Two video cameras were setup to record the entire simulation process. Two observers reviewed the video records independently to identify the start and end of each CPR-intubation sequence, any intubation attempts, and the hands-off and compression segments of each sequence. Disagreements were resolved by reaching mutual consensus. The HQCPR application on an Android device recorded chest compression depth, rate, and interruptions (defined as no chest compression [hands off] for >1 s). The data from both the video recording and the HQCPR application were used in subsequent analysis. Continuous data are presented as medians with interquartile ranges, and categorical data are presented as frequency counts and percentages. The continuous data were compared using the Wilcoxon rank sum test in the first CPR-intubation sequence and the Mann-Whitney U test in the second and third sequences. The McNemar test was used to compare the intubation success rate in the first sequence, and Pearson's chi-square test was used for the second and third sequences. The continuous data from all three CPR-intubation sequences were compared using the Kruskal-Wallis test. Post hoc analysis was performed using Conover's test.

The association of CPR quality metrics with successful intubation was evaluated using a Cox proportional hazards regression model. The results of multivariate analyses are presented as hazard ratios (HRs) with corresponding 95% confidence intervals (CIs). A two-tailed $P < 0.05$ indicates statistical significance. MedCalc Statistical Software version 19.2. (MedCalc Software, Ostend, Belgium) was used for data analysis.

Effect :

understand the impact of airway vomitus on CPR quality and intubation quality

Key words :

Cardiopulmonary resuscitation, Airway decontamination, suction assisted, vomiting simulation

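### Each EMT-P does both scenarios in turn, but random or balanced order is not provided for and the named scenario tests have no period term, so practice or fatigue can bias the contrast if the order was uneven

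*Protocol*

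**What the plan says.** Everything relevant stands in the Methods section of the protocol synopsis. The design is described as "This is a prospective compare study". On participants it says "54 EMT-Ps, are involved to evaluate the impact of airway management on CPR quality", and on teams "Three EMT-Ps formed a resuscitation team and played one of the following roles"; each EMT-P takes all three roles within each scenario.

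On order there are two sentences: "All EMT-Ps were assigned to participate initially in one of the scenarios", then "After all EMT-Ps had finished the first scenario, they switched to the other". No method of assignment, ratio or balance is given. The only mention of randomisation in the document, in the Background, concerns earlier trials.

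The analysis paragraph then fixes the scenario tests. "The continuous data were compared using the Wilcoxon rank sum test in the first CPR-intubation sequence", with Mann-Whitney for the second and third sequences. "The McNemar test was used to compare the intubation success rate in the first sequence", with Pearson's chi-square for the later ones. The Cox model relates CPR metrics to successful intubation and is not an analysis of the scenario contrast in the primary outcomes.

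**The concern.** The design is a two-period crossover on a manual skill. Before the switch, each EMT-P has rotated through compression and intubation on the same manikin. Performance may then improve with practice or decline with fatigue, whichever scenario comes second.

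A crossover protects against this in two ways: both orders are used in equal numbers, preferably at random, and the analysis allows for period. The protocol provides for neither. If the order was uneven, the named tests cannot separate the effect of regurgitation from the effect of going second. A difference in chest compression fraction, depth, rate or longest interruption could then be inflated or masked, and measuring that difference is the study's stated objective.

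**Working it through.** The plan gives no power calculation, effect size or SD, so there is no figure of its own to reproduce.

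**Inputs from the protocol.** 54 EMT-Ps in threes, so 54/3 = 18 teams; two scenarios per EMT-P; two-sided 5% level; tests as named.

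**Inputs assumed.** Period effect 0.2 or 0.5 SD; within-person correlation 0 to 0.5; order assigned by whole team; same trios in both periods; one first sequence per airway manager per scenario, hence 54 against 54; no unequal carry-over unless stated.

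**Bias.** Let τ be the scenario effect (regurgitation minus clean), π the period effect (second minus first), n1 the teams starting clean and n2 the teams starting with regurgitation. The expected within-person difference, regurgitation minus clean, is τ + π in clean-first teams and τ − π in the others. Averaged over all teams it is

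τ + π × (n1 − n2)/18.

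- 18:0 gives 18/18 = 100% of π
- 15:3 gives 12/18 = 67%
- 12:6 gives 6/18 = 33%
- 9:9 gives 0

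If the order was assigned to individual EMT-Ps and trios changed, the same formula holds with 54 in the denominator and counts of EMT-Ps.

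**False-positive rates.** Simulated with normal data, no scenario effect and 5000 runs per setting. The ranges run over the assumed correlations.

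| Split | Rank-sum, π = 0.2 SD | Rank-sum, π = 0.5 SD | Signed-rank, π = 0.2 SD | Signed-rank, π = 0.5 SD |
|---|---|---|---|---|
| 18:0 | 10–17% | 71–78% | 16–28% | 70–95% |
| 15:3 | 4–10% | 34–38% | 10–16% | 36–61% |
| 12:6 | 1–6% | 6–12% | 6–8% | 11–17% |
| 9:9 | 1–5% | 0.5–4% | 4–5% | 3–4% |

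The signed-rank columns are shown because the paired McNemar test named beside the rank-sum test may mean that a paired test was intended. The bias is the same either way. Rank-sum rates far below 5% at 9:9 come from ignoring a positive within-person correlation, which costs power.

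**An analysis that removes the period effect.** Take period 2 minus period 1 and average it by team. Its expectation is π + τ in clean-first teams and π − τ in regurgitation-first teams. The difference between the order groups is 2τ, so half of it estimates τ. With a true effect of 0.5 SD, the unhalved contrast came out at 0.99–1.00 in simulation. With no scenario effect, a t-test on the 18 team values rejects 4.3–5.5% of the time at 15:3, 12:6 and 9:9.

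**Limit of that analysis.** If starting with regurgitation carries over differently from starting clean, balance does not help. With an assumed extra carry-over after regurgitation-first at 9:9 and no scenario effect, the t-test rejects 8–11% of the time at 0.2 SD and more than 20%, up to about 42%, at 0.5 SD.

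**The case against.** The strongest reply is that this is silence rather than error. The document is a synopsis, it does not say that the order was uneven, and it does not rule out randomisation. Being assigned to one of two scenarios and later switching reads naturally as a split start. With an even split there is no bias under the model above, and at 12:6 with a small period effect the rank-sum test stays near its nominal level. Every large figure needs both a lopsided split and a sizeable period effect, and the document gives neither.

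Much of this stands. A reader might infer that all teams began with the same scenario, or that the order was not randomised. The text supports neither inference: its wording fits a split start and a common start alike, and it says nothing on the method of assignment. The 18:0 row is a worst case, not a description of the study.

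What does not stand is that the matter can be left to an unseen SAP. Allocation of order is part of the design, and the protocol deals with it by the single word assigned. The protocol also names the tests itself, and none of them could correct an uneven split.

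It is also fair to say that an exact 9:9 split is better practice rather than a condition of validity. A fair coin toss per team would give 12:6 or worse with probability 0.238, and the order-stratified analysis remains valid there.

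**Conclusion.** The concern holds as a weakness of design and analysis, not as proof that the results are biased. The protocol sets up a crossover on a skill task, does not provide for random or balanced order, and fixes scenario tests that cannot allow for period. The possible bias runs from none to the whole period effect, in proportion to the order imbalance, and its direction is unknown. The conclusion that the tests cannot separate scenario from period under an uneven order follows from the text. The error rates rest on the assumed period effects and correlations. Exact proportionality applies to the mean difference; the rank tests move in the same direction. The change is worth making because it is cheap, and because without it a reader cannot tell how much of a difference is due to regurgitation.

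**What to change.** **Design.** Randomise the 18 teams in a fixed 9:9 split to clean-first or regurgitation-first, keep the same trios in both periods, and say so in Methods. If sessions are complete, as the past tense may suggest, report how the order was assigned and the split that resulted.

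**First sequence, continuous outcomes.** Replace the rank-sum test by a paired, order-stratified comparison. Average the period-2-minus-period-1 differences by team, compare them between the two order groups (t-test or Mann-Whitney), and report half of the between-group contrast, with its interval halved too, as the scenario effect. The alternative is a mixed model with scenario and period as fixed effects and person and team as random effects; this is the one to use if trios changed at the switch.

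**First sequence, intubation success.** Replace McNemar by an order-stratified paired binary test, such as Mainland-Gart, or by a logistic mixed model with scenario and period.

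**Statements to add.** The result assumes no unequal carry-over between the two orders. If all teams used one order, scenario and period effects cannot be separated by any analysis.

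**Cost.** An allocation list of 18 entries and a few changed sentences in the analysis paragraph; if sessions are complete, only reporting and analysis change. The team-level t-test has 16 degrees of freedom. Against a paired t-test on 54 differences (53 degrees of freedom; not a test the protocol names), the critical value rises by 2.120/2.006 = 1.057, about 6%. A 12:6 split costs √[(1/12 + 1/6)/(1/9 + 1/9)] = 1.061, a further 6% in standard error against 9:9.

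Power is not assured. For an assumed 0.5 SD scenario effect at 9:9, the t-test on team values has 93% against 75–76% for the rank-sum test at within-person correlation 0.5, and 68% against 68–70% at correlation 0. If differences also correlate 0.5 within teams, the figures are 68% against 68–71%, and 41% against 65–66%. In that last case the rank-sum test's apparent advantage comes with a false-positive rate of 15–16%.

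### Each run has a defined final result, but success is compared only sequence by sequence: final success goes untested, and the sequence 2 and 3 tests compare selected subsets

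*Protocol*

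**What the plan says.** The Protocol's Methods set three rules for a run.

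- Retry: "If intubation was not successful, the airway manager performed BVM ventilation twice and then reattempt intubation".
- Stop: "Each simulation was ended after successful or failed intubation".
- Failure: "Failed intubation was defined as either oesophageal intubation or three unsuccessful attempts".

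The outcome list then says: "The secondary outcomes were the intubation success rate and intubation time". It gives no unit for the success rate, neither attempt, sequence nor run.

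The statistical paragraph of the Methods chooses the tests: "The McNemar test was used to compare the intubation success rate in the first sequence". For the two later sequences it names a Pearson chi-square test instead. Two other analyses come near the subject, but neither compares final success between the scenarios. Kruskal-Wallis is reserved for continuous data. The regression model is described thus: "The association of CPR quality metrics with successful intubation was evaluated using a Cox proportional hazards regression model". Categorical data are to be shown as counts and percentages.

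**The concern.** The stopping and failure rules give every run one of two endings: a placed tube, or failure by oesophageal intubation or a third miss. Success is tested only at the level of the sequence, and this has two consequences.

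First, a run reaches sequence 2 or 3 only if it has neither succeeded nor ended in oesophageal intubation. If soiling changes either probability, the two scenarios send different and differently sized subsets of runs into the later sequences. A chi-square test there does not compare like with like.

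Second, in sequence 1 an oesophageal placement that ends the run counts the same as a miss that can be retried. If soiling turns retryable misses into final failures, the sequence-level rates can stay similar while more soiled runs end without a placed tube. No named test addresses that difference, although the success rate is a named secondary outcome and the Effect paragraph promises information on intubation quality.

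**Working it through.** **No figure to reproduce.** The protocol gives no expected success rate, oesophageal rate or power. All rates below are assumptions.

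**Pairs available (Methods).** There are 54 EMT-Ps in teams of three, so 54 / 3 = 18 teams. Each member takes each role once per scenario, giving 18 x 3 = 54 runs per scenario. Everyone does both scenarios, so there are 54 pairs by airway manager for any result that every run has. First-sequence success and final success are both such results; sequence 2 and 3 success is not.

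**Formula.** Let s be the success probability per attempt, o the oesophageal probability per attempt, and r = 1 - s - o the probability of a retryable miss. One sequence is taken as one attempt. Then:

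- runs entering sequences 1, 2 and 3: 54, 54r, 54r²
- final success: s(1 + r + r²)

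**Same per-attempt success, different oesophageal rates (s = 0.70 in both scenarios).**

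| Oesophageal rate | r | Runs entering sequences 1/2/3 | Final success |
|---|---|---|---|
| 2% | 0.28 | 54 / 15.1 / 4.2 | 0.70 x 1.3584 = 95.1% |
| 20% | 0.10 | 54 / 5.4 / 0.5 | 0.70 x 1.11 = 77.7% |
| 5% | 0.25 | 54 / 13.5 / 3.4 | 0.70 x 1.3125 = 91.9% |
| 15% | 0.15 | 54 / 8.1 / 1.2 | 0.70 x 1.1725 = 82.1% |

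At 2% v 20% the gap is 17.4 points, or 0.174 x 54 = about 9 runs. At 5% v 15% it is 9.8 points, or about 5 runs. Success within every sequence is 70% v 70% throughout, and the later denominators differ between scenarios and become very small.

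**Power of exact McNemar, 54 pairs, two-sided 0.05.** With final success Pc (clean) and Ps (soiled), and independence within pairs assumed, the discordant probabilities are Pc(1 - Ps) and Ps(1 - Pc). The number of discordant pairs is binomial on 54, and their split is tested against one half.

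| Success per attempt, clean v soiled | Oesophageal rate, clean v soiled | Power, first-sequence success | Power, final success |
|---|---|---|---|
| 70% v 70% | 2% v 20% | about 3% | about 68% |
| 70% v 70% | 5% v 15% | about 3% | about 23% |
| 70% v 70% | 5% v 10% | about 3% | about 8% |
| 85% v 60% | 2% v 15% | about 78% | about 83% |
| 90% v 65% | 2% v 10% | about 84% | about 53% |
| 90% v 60% | 5% v 5% | about 94% | about 12% |

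In the first three rows first-sequence success does not differ, so the 3% is only the false-positive rate of the exact test. In the last three rows soiling lowers first-pass success. The first-sequence test is then strong, and in two of the three it is the stronger one.

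**The case against.** The best defence is that nothing here is contradictory. The failure sentence follows the stopping rule and serves to say when a run ends. The secondary outcome has no stated unit, and the statistical paragraph supplies one, the sequence, which is also the unit for chest compression fraction and longest interruption. First-sequence success is a legitimate outcome, and it is the one the Background motivates. All of this stands.

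Final success is also not hidden if counts are shown by sequence. In the 2% v 20% example the expected successes sum to 37.8 + 10.6 + 3.0, about 51.3 before rounding the terms, against 37.8 + 3.8 + 0.4 = 42.0. Oesophageal failures in sequence 1 follow as 54 minus successes minus runs entering sequence 2: 54 - 37.8 - 15.1 = 1.1 v 54 - 37.8 - 5.4 = 10.8. This stands too, with one limit: summed counts give the two proportions but not the paired table that a McNemar test needs.

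A reader might infer that the planned tests would miss the effect of soiling on intubation. The documents do not support that. The contrast of 68% v 3% needs equal per-attempt success and a tenfold difference in oesophageal rate, whereas the Background says that soiling considerably lowers first-pass success. Nor are oesophageal failures the only runs to leave: successful runs leave as well, and an oesophageal placement is properly counted as a non-success in its own sequence.

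Finally, an unseen statistical analysis plan could add a comparison of final success. But the protocol itself selects the tests for this outcome, including the later-sequence tests on selected subsets.

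**Conclusion.** The point holds in a limited form. First-sequence success is compared validly on all 54 pairs. The sequence 2 and 3 chi-square tests compare subsets selected by what happened earlier in the run, so they are not valid scenario comparisons of intubation success. Final success, which the stopping and failure rules define for every run, has no named comparison even though a paired result exists for all 54 EMT-Ps.

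The size is unknown. Under the assumed 70% per-attempt success in both scenarios, the untested gap in final success is 17.4 points at oesophageal rates of 2% v 20% and 9.8 points at 5% v 15%. The added test would detect these with power of about 68% and 23%, so it is no guarantee either.

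It would go too far to conclude that final success is the correct endpoint and should displace first-pass success. The protocol does not state the unit of the success rate, and the first-sequence test is often the more sensitive when first-pass success falls.

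The conclusion assumes one sequence per attempt. The rules for the start and end of a sequence are not shown, but this reading fits the three-attempt limit and the change from a paired to an unpaired test after the first sequence. Only a secondary outcome is touched and the primary CPR metrics are unaffected, so the severity is minor.

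**What to change.** In the outcome definitions and the statistical paragraph of the Methods:

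1. Name first-sequence success as first-pass success and keep McNemar on all 54 pairs.
2. Add final success per run as a second named measure, using the failure definition already in the Methods, and compare it between scenarios with McNemar on all 54 EMT-P pairs.
3. Drop the chi-square tests of success in sequences 2 and 3. Report those rates descriptively, with the number of runs entering each sequence.
4. Report the number of oesophageal intubations per scenario.
5. State that one sequence corresponds to one attempt, if that is what is meant.

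The cost is some wording and one extra paired 2x2 table. Both cameras already record every attempt, so no new data are needed and no procedure changes. The downside is one more secondary comparison, partly offset by removing the two later-sequence tests of success.

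### Two of the four primary outcomes rest on segments marked from video with no masking described, and the protocol does not say whether video or the HQCPR log governs them.

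*Protocol*

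**What the plan says.** All of this stands under Methods in the protocol synopsis.

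- Primary outcomes: "The primary outcomes were CPR quality metrics, namely chest compression fraction (CCF), chest compression depth, chest compression rate, and longest interruption time".
- Definitions: "CCF was defined as the proportion of time spent on chest compression in each CPR-intubation sequence", and "The longest interruption time was defined as the longest hands-off duration in each sequence". Neither gives a minimum pause length.
- Video: "Two video cameras were setup to record the entire simulation process". From it the segments are marked: "Two observers reviewed the video records independently to identify the start and end of each CPR-intubation sequence, any intubation attempts, and the hands-off and compression". Then: "Disagreements were resolved by reaching mutual consensus". Masking of the observers to scenario is not mentioned.
- Device: the HQCPR application "recorded chest compression depth, rate, and interruptions (defined as no chest compression [hands off] for >1 s").
- Use of the two sources: "The data from both the video recording and the HQCPR application were used in subsequent analysis". No outcome is assigned to a source, and no order of precedence is given.

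**The concern.** The manikin regurgitates in one scenario only, and an attempt is timed from the blade entering the mouth to its leaving it. An observer who times the blade must look at the mouth and so will almost certainly know the scenario. The Background sets an expectation: gastric fluid obscures the laryngeal view, and intubation brings multiple and prolonged CPR pauses. If that expectation affects where pauses are judged to begin and end, the error runs in one direction, towards worse CPR in the soiled airway. Two independent readings reduce random error. Consensus then settles differences between the observers, but it does not touch an error they have in common.

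The study already collects a record of interruptions that needs no judgement about pause boundaries. The text does not say whether that record or the video supplies CCF and longest interruption, or which prevails when they disagree. It also leaves open whether a pause of 1 s or less counts as hands-off on video. Two analysts with the same data could reach different CCF values, and the choice of source could vary between runs.

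**Working it through.** The protocol gives no expected CCF, SD, sequence length or number of pauses, so there is no stated figure to reproduce. The text is checked first. The sizes after it are illustrations on assumed inputs.

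**Step 1: what each source supplies.**

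| Quantity | Video observers | HQCPR application |
|---|---|---|
| Sequence start and end | yes | not described |
| Intubation attempts (blade in, blade out) | yes | not described |
| Hands-off and compression segments | yes, no threshold stated | interruptions, >1 s |
| Depth and rate | no | yes |

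The overlap is in the third row, which determines CCF and longest interruption. Depth and rate come from the device, although the windows over which they are summarised may still be set by the observers.

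**Step 2: marking shift.** CCF change in points = 100 × (pauses × seconds shifted per pause) / sequence length. Assume 0.5 s per pause, that is 0.25 s at each of its two boundaries.

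| Sequence length (assumed) | 1 pause | 2 pauses | 4 pauses |
|---|---|---|---|
| 30 s | 1.7 | 3.3 | 6.7 |
| 60 s | 0.8 | 1.7 | 3.3 |
| 120 s | 0.4 | 0.8 | 1.7 |

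Example: 100 × (4 × 0.5) / 60 = 3.3 points. Longest interruption moves by the shift on that one pause, here 0.5 s.

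**Step 3: threshold.** Suppose each short pause lasts up to 1 s and counts as hands-off on video but not under the >1 s rule. The largest CCF difference is 100 × (pauses × 1 s) / sequence length.

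| Sequence length (assumed) | 1 pause | 3 pauses | 5 pauses |
|---|---|---|---|
| 30 s | 3.3 | 10.0 | 16.7 |
| 60 s | 1.7 | 5.0 | 8.3 |
| 120 s | 0.8 | 2.5 | 4.2 |

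These are ceilings. For longest interruption, dropping pauses of 1 s or less leaves the maximum unchanged whenever the maximum exceeds 1 s, so the threshold bears in practice on CCF only.

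**Step 4: consequence for the test.** Each of the 54 EMT-Ps is airway manager once per scenario, giving 54 pairs in the first sequence. With no true difference, a marking bias of b points and an SD of paired differences s, the normal approximation at two-sided 0.05 gives

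P(reject) = Φ(d − 1.96) + Φ(−d − 1.96), with d = b√54 / s.

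For b = 1 and s = 10: d = 0.735, so P = Φ(−1.225) + Φ(−2.695) = 0.11.

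| Bias (assumed) | SD 5 | SD 10 | SD 15 |
|---|---|---|---|
| 1 point | 0.31 | 0.11 | 0.08 |
| 2 points | 0.84 | 0.31 | 0.17 |

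This treats the 54 pairs as independent, although they come from 54 / 3 = 18 teams, and it stands in for the planned rank test. It shows the order of size only.

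**The case against.** The strongest reply is that whether hands are compressing a chest is a plain physical event, read by two people independently, and that nothing in the protocol shows either of them moving a boundary because of the scenario. That is fair: the bias is a risk of the design, not an observed fact, and even the visibility of the vomitus is inferred.

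A reader might infer that the device and the video apply different rules. The text does not support this. It states >1 s for the application and attaches the term hands-off to it, the same term used for the video segments. The limit may have been meant for both. In addition, a sentence on the rules for sequence start and end has lost its subject and probably pointed to a figure or table that is not shown. As described, that item covers sequence boundaries, but it may have held more.

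A reader might also infer that both sources feed the same outcome. The text says only that data from both were used. Taking depth and rate from the device and all timing from video is a natural reading. It would settle the source, but it would leave the two outcomes wholly with observers for whom no masking is described.

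Finally, a threshold applied alike in every run shifts both scenarios. It biases the comparison only if short pauses are more frequent in one scenario, or if the source varies between runs.

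What survives is the absence of described masking, the missing source rule and the unstated video threshold. Assigning a derived variable to a source can be left to an SAP. Who measures a primary outcome, and from what, is something this document does set out, and it does so incompletely.

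**Conclusion.** The point holds as a weakness in how two primary outcomes are measured, and it should be corrected. CCF and longest interruption time depend on segments marked from video without described masking, while a device record of interruptions sits beside them with no stated role in those outcomes.

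The size is uncertain. A modest marking shift is worth about 1 to 3 points of CCF in a 60 s sequence. The threshold is worth at most about 1 to 17 points across the assumed range, and the upper end needs five pauses, each close to 1 s, within 30 s. Shifts of 5 to 10 points from marking alone would need short sequences, many pauses and every boundary moved the same way in one scenario. That is a worst case, not an expectation. Even so, a bias of 1 or 2 points could matter for the test if paired differences vary little.

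The documents do not support saying that the results are biased, that the two sources use conflicting rules, or that the threshold affects longest interruption in practice.

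**What to change.** State one source and one rule for both scenarios:

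1. Take hands-off time from the HQCPR log under its >1 s definition in every run. It gives longest interruption directly and the CCF numerator as sequence length minus hands-off time.
2. Use video only for sequence start and end and for blade-in and blade-out times.
3. Where the log is missing or cannot be aligned with the video, mark the segments from video under the same >1 s rule. If the camera framing allows, do so with the airway out of view and the scenarios in mixed order. Report how many runs were handled this way.

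The cost is the work of synchronising a log and recordings that the study already collects, plus some extra reading where the fallback is needed. The fix relies on a time-stamped log, which the protocol does not describe. If there is none, step 3 becomes the main method. Sequence boundaries, and so the CCF denominator, remain set by observers who can probably see the scenario. The change therefore removes most of the observer judgement, but not all of it.
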